1. Cannabis: CBD may cause somnolence, decreased appetite, diarrhea; fatigue, malaise, asthenia and poor quality sleep. The THC may cause intoxication. Participants are instructed to take the THC in the evening to help with sleep. Risks of THC include sedation, gait disturbance, tiredness, anxiety, concentration difficulties, dizziness, sleep disturbance, changes in food intake, restlessness, confusion, sleepiness, headache, nausea, dry mouth, pallor, flushing, sweating, and slurred speech.

Subjects will be called the morning after taking the first cannabis dose to inquire about any side effects they may have experienced. If a volunteer reports side effects other than tiredness and sleepiness we will discuss reducing the dose of THC at bedtime. Subjects will be informed that taking capsules shortly after a heavy meal may increase intoxication relative to a lighter meal. The volunteers will be informed that they should contact the PI between study visits if needed due to concern over side effects. During the weekly visits, participants will be asked about side effects.

There have been reports that smoking cannabis increases the risk of heart attack in patients with established heart disease. The risk of this with oral cannabinoids is not known, but subjects with cardiovascular disease will be excluded. Smoked cannabis can also cause increased heart rate and hypotension, and we will exclude volunteers with orthostatic hypotension. Due to the potential for cannabis to affect warfarin metabolism, subjects taking this drug will be excluded.

2. Risks associated with the psychological test battery include potential nervousness and frustration with the tasks. A member of the research team will carefully explain the tests before hand and will be available for questions during the tasks should they arise. Subjects will be informed that they can stop if they choose to.
3. COVID-19. There is risk of exposure to coronavirus 2019 (COVID-19) related to travel for research purposes and to the in-person visit to NYSPI. We will do everything that we can, in concordance with NYSPI policy, to minimize risk to research participants and staff posed by COVID-19.

Methods to Protect Confidentiality

Describe the data management plan and the methods you will employ to protect subject privacy and the confidentiality of research data. The section should detail how information will be collected, recorded, coded, stored, transmitted, and as applicable, shared with other investigators so as to minimize risks related to breach of confidentiality. Confirm that identifiers are removed, to the extent possible, from research data, and explain if there are links between subject identity and research data, or if the data is anonymous. Also, indicate where the data is stored, who is responsible for its

safekeeping, and who has access to subject identity and codes, if any, which cross-link research data and subject identity. Confirm that identifiable data is not collected, stored, or transmitted by mail, fax, on removable drives, laptops, or via the internet without proper protections, e.g. encryption.

Participants divulge information which is sensitive and may have adverse social consequences if released. We deal with issues of confidentiality by using coded records, storing signed consent forms in a locked cabinet, and try to the best of our ability to maintain confidentiality. Data are kept on a password-protected computer, and if there is any electronic transmission concerning the study, it will use numeric identifiers rather than participant names. We also point out to prospective participants that we cannot assure that their medical histories and other personal records might not become known. In addition, we inform volunteers that we must conform with NY State reporting requirements. In addition to a discussion of this topic, the information is clearly stated in our consent forms.

Following the NYSPI Remote Communications Guidance, confidentiality of remote communication is protected through the use of secure HIPAA compliant telecommunication (e.g. Webex, Facetime, or telephone) in combination with digital data collection procedures (through remote access to secure NYSPI systems and encrypted email).

Direct Benefits to Subjects

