Concisely state the objectives of the study and the hypothesis or primary research question(s) being examined. There should be one hypothesis for every major study procedure or intervention. For pilot studies, it is important not to overstate the study's objectives. If there are no study hypotheses, describe broad study goals/aims.

Aim 1: Effect of cannabis on pain and numbness in TIPN. Breast cancer patients with TIPN who have an interest in participating in a placebo-controlled trial of cannabis will be recruited. The volunteers will be randomized into two groups: active cannabis product (n=48) versus placebo (n=48). The active cannabis group will receive up to three capsules a day containing 100 mg of CBD and 5 mg of THC, for a maximum total of 300 CBD and 15 mg THC. The doses will be titrated up and subjects will take the dose they tolerate best. The placebo condition contains negligible levels of CBD and THC (<0.1 mg). The cannabis will be provided by Tilray, Inc. We hypothesize that subjects receiving the active treatment will experience an improvement in neuropathy symptoms, measured with the change in BPI-SF (for pain) and FACT/GOG-Ntx scores (to measure paresthesia, numbness, and function).

Aim 2: Effect of cannabis on sensory deficits and tactile acuity in TIPN. These outcome measures will be obtained in the same subject groups to assess additional measures of neuropathy: 1) the tactile acuity cube, used to assess spatial acuity; and 2) mechanical sensitivity measured with von Frey filaments. We will also measure sleep and changes in medication. Our hypothesis is that the active group will experience an improvement in these measures over the placebo group.

Inclusion/Exclusion Criteria

This section details your study sample(s) and addresses the requirement for risk minimization.

You may choose to divide your sample by population (healthy controls vs. subjects) or by procedure (subjects who will have an MRI) and then define different sets of criteria for each.

For each sample, create or insert a table to describe detailed criteria for study inclusion and exclusion and the method you will use to ascertain each criterion. The method of ascertainment may describe tests, scales and instruments. When

relevant, indicate the level of training of the person who will make the assessment (e.g. clinical interview by a psychiatrist).

Inclusion/Exclusion Criteria needs to be numbered and listed in outline form (see Table template below).

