CRITERION	METHOD OF ASCERTAINMENT
Inclusion:	
1. Participants with breast cancer (stage I, II or III), experiencing TIPN due to paclitaxel or docetaxel, who have completed chemotherapy. Participants must have an ECOG score, which measures level of function, of 2 or better. Participants must have a score of 2 or 3 score for sensory neuropathy, as assessed by the Common Toxicity Criteria Adverse Events (CTCAE).	Medical Assessment, interview with study clinician, Eastern Cooperative Oncology Group (ECOG) scale and Common Toxicity Criteria Adverse Events (CTCAE) scale. The ECOG (range 0 to 5) describes a patient's level of functioning in terms of their ability to care for themselves, daily activity, and physical ability. The CTCAE describes the severity of toxicity for patients receiving cancer therapy (range 0 to 5). Subjects are required to have a score on the neuropathy sensory scale of 2 (sensory alteration or paresthesia, interfering with function, but not interfering with activities of daily living) or 3 (sensory loss or paresthesia interfering with activities of daily living), but not above.
2. Able to give informed consent and comply with study procedures.	Medical Assessment, interview with a study clinician.
3. Ages of 21-60.	Medical Assessment, interview with a study clinician, intake questionnaire.
Exclusion:	
1. Meet DSM-V criteria for current major psychiatric illness, such as bipolar disorder, major depression, or psychosis. Subjects with a current substance use disorder will be excluded.	Medical Assessment, interview with study clinician. Score of ≥ 17 on the Hamilton Depression Rating Scale. Urine toxicology screen (for cannabis, opioids, cocaine, amphetamines).
2. Diagnosis of a major medical or neurological disorder, including hypertension or orthostatic hypotension, cardiovascular	Medical Assessment, laboratory studies, interview with a study physician.

disease, or neurodegenerative disorders (movement disorders, dementia) that would exclude cannabinoid use. Subjects with renal or hepatic impairment will not be included. Subjects with a history of peripheral neuropathy resulting from other causes will be excluded. Subjects taking warfarin will also be excluded.
		

3. Current use of cannabis
	
Medical Assessment, urine toxicology, interview with a study clinician
	

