In order to reduce in-person contact, there will be two screening visits. The first visit will be done using Webex and/or telephone. This visit will include the physicians' assessment (medical, psychiatric history, review of medications); the assessments (listed above), and a review of inclusion and exclusion criteria with the subject. Of subjects who meet criteria, based on the virtual visit, an in-person screening visit will be done. This includes the ECG, physical exam, pregnancy test, and lab work. If subjects already have lab work (from their primary care doctor or oncologist) they will be asked to bring it to the in-person screening visit.

Study Entry

Once the subject is entered into the study they will perform a baseline (pre medication) visit, followed by weekly visits for 8 weeks.

In the event that a subject attends the in-person screening visit and has a normal ECG, normal physical exam, and normal labs (brought with them), we will combine the in-person screening visit and the baseline visit into one lab visit.

The outcome measures and procedures for each visit are included here:

- 1) The Brief Pain Inventory-Short Form (BPI-SF), a short, self-administered questionnaire using a 0 to 10 scale, developed to quantify measures of pain (23).
- 2) The Functional Assessment of Cancer Therapy Taxane (FACT/GOG-TAX) and the 38-item neurotoxicity score (FACT-NTX), which asks about Quality of Life, well-being, in addition to neuropathy specific questions about and discomfort, numbness, tingling, and functional changes (trouble feeling small objects in hand or trouble walking) (24).
- 3) Promis Sleep Questionnaire: The 8-item Patient-Reported Outcomes Measurement Information System (PROMIS™) Sleep Disturbance questionnaire has been developed by the American Psychiatric Association as part of the NIH Roadmap Initiative. It is a 5-point Likert scale(1 = "not at all," 2 = "a little bit," 3 = "somewhat," 4 = "quite a bit," and 5 = "very much") where participants will rate 8 measures of sleep over the past 7 days.

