- 4) Medication Questionnaire: Participants will be asked to report on the medication use at baseline and at the weekly visits, including the dose, schedule, and any side effects. Adjuvant drug use will be assessed at study completion using an ordinal rating scale that indicates whether the doses are unchanged, increased, or decreased. The presence of additional drugs would be graded as an increase, whereas discontinuing a drug would be graded as a decrease in analgesic/adjuvant dose.
- 5) Mechanical sensitivity using von Frey filaments (2.83, 3.61, 4.31, 4.56, 5.07 and 6.65) purchased from North Coast Medical (Gilroy, CA). Beginning with the smallest size, the filament will be applied to the palm of the hand that is most affected, or the dominant hand is the neuropathy is the same bilaterally. For each filament size, four positive trials and one negative trial (no touching of skin) will be performed. The mechanical sensitivity threshold is the filament size where the subject reports three correct answers on the positive trial and is correct on the one negative trial.
- 6) The Tactile Acuity Cube (TAC) test will be used to assess spatial acuity, as described previously (25). The cube is comprised of 6 sides each containing a grating with widths of increasing size (from 0.75 mm to 6.0 mm). Shielded glasses will be used as subjects are asked to turn up the palms of the dominant hand on a table. The gratings of the cube will be applied for 2 seconds to the finger pad of the index finger and the subject will be asked to say whether the grating is vertical or horizontal to the long axis of the finger. A narrower grating will be used if the subject answers correctly, and a wider grating if the subject answers incorrectly.

The schedule for the scales and tests at laboratory visits is as follows:

Visit	Scales (items 1 to 4, above)	In person lab visit	TAC	Mechanical Sensitivity	Blood levels
Baseline	x	x	x	x	

Week #1	x				
Week #2	x	X*	x	x	
Week #3	x				
Week #4	x	x	x	x	x
Week #5	x				
Week #6	x	X*	x	x	
Week #7	x				
Week #8	x	x	x	x	x

In order to reduce in-person contact, the visits on weeks 2 and 6 are optional (X*). Participants can opt out of these in-person visits if they wish. However, participants will be asked to decide ahead of time about attending these visits, so that the appropriate amount of drug is dispensed.

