- 6) The Tactile Acuity Cube (TAC) test will be used to assess spatial acuity, as described previously (25). The cube is comprised of 6 sides each containing a grating with widths of increasing size (from 0.75 mm to 6.0 mm). Shielded glasses will be used as subjects are asked to turn up the palms of the dominant hand on a table. The gratings of the cube will be applied for 2 seconds to the finger pad of the index finger and the subject will be asked to say whether the grating is vertical or horizontal to the long axis of the finger. A narrower grating will be used if the subject answers correctly, and a wider grating if the subject answers incorrectly.

Research Related Delay to Treatment

Research involving participants who are in need of treatment invariably involves delay to care, and this delay is associated with risk. Scheduling of procedures must be carefully organized to minimize delay. Other delay must involve only that minimally necessary to accomplish the aims of the research while respecting subject well-being and safety. Describe the delay, by virtue of research participation in this study, before a participant can receive treatment of known efficacy or standard care routinely offered in the community.

There is no delay to treatment and subjects will continue their regular care.

Clinical Treatment Alternatives

Describe what other treatment or assessment options are available to subjects who do not participate in research.

Other treatments for CIPN include duloxetine.

Risks/Discomforts/Inconveniences

"Risk" is a broad term used to convey the potential for harm, burden, and inconvenience related to research participation. Use this section to provide a comprehensive description of foreseeable physical, psychological, social, interpersonal, and economic risks introduced by the research. Include the source of the information. Consider both the probability and magnitude of harm and its impact. Describe the foreseeable harms associated with the research (untoward effects of a medication) and those related to delay to individualized treatment. Include data from the literature, and local data, if available, on risk rates and subject experiences with research procedures. Describe procedures in place to minimize risk. In general, please create a numbered list of risks/categories of risk, and in general put the list in the order of significance or level of risk, the most significant risks first followed by others.

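### The two Aim 2 sensory tests are done only on a hand and by different hand rules, while entry does not require hand involvement, so some participants can be tested where they have little or no deficit

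*Combined protocol and SAP*

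**What the plan says.** Specific Aims and Hypotheses, Aim 2, names the sensory measures: "1) the tactile acuity cube, used to assess spatial acuity; and 2) mechanical sensitivity measured with von Frey filaments". Its hypothesis is that "the active group will experience an improvement in these measures over the placebo group".

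The procedures are under Study Entry, items 5 and 6, and are repeated under Assessment Instruments.

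- **Von Frey (item 5):** "the filament will be applied to the palm of the hand that is most affected", with the dominant hand as the fallback when both sides are the same.
- **Tactile cube (item 6):** "Shielded glasses will be used as subjects are asked to turn up the palms of the dominant hand on a table". The site on that hand is also fixed: "The gratings of the cube will be applied for 2 seconds to the finger pad of the index finger". Nothing provides for the other hand being worse.

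On neuropathy, the inclusion criterion reads "Participants must have a score of 2 or 3 score for sensory neuropathy, as assessed by the Common Toxicity Criteria Adverse Events (CTCAE"). The grades, set out there and again under Screening and Recruitment, are defined by interference with function or daily activities, not by hand or foot. The neurotoxicity questionnaire covers both sites, listing "functional changes (trouble feeling small objects in hand or trouble walking").

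The Statistical Analysis section applies Aim 1-type models (change from baseline, adjusted for the baseline value) to the Aim 2 measures. It sets no minimum baseline deficit and no analysis set based on hand involvement. It also lists vibration threshold and corneal nerve fibre length. However, no vibration procedure is described, and corneal microscopy belongs to an optional separate study. Neither supplies a scheduled sensory test at the foot.

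**The concern.** A test can show recovery only where there is something to recover. Item 5 accepts this principle by following the affected hand. Item 6, directly below it, uses handedness instead and gives no reason. Entry does not guarantee that either hand is affected.

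What is at stake is the sensitivity of the two Aim 2 sensory measures. If some participants are tested on skin with little or no deficit, the average difference between arms shrinks. A null result could then mean that the treatment does not restore sensation, or that the tests were partly done in the wrong place. If the site of neuropathy is not recorded at baseline, the two explanations will be hard to separate later.

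**Working it through.** **Step 1. Apply the two rules to each pattern of neuropathy that entry allows.**

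| Pattern at baseline | Von Frey hand | Cube hand | Consequence |
|---|---|---|---|
| Both hands equally affected | Dominant | Dominant | Same hand, affected |
| Dominant hand worse | Dominant | Dominant | Same hand, affected |
| Non-dominant worse, dominant also affected | Non-dominant | Dominant | Cube on the less affected hand |
| Non-dominant hand only | Non-dominant | Dominant | Cube on an unaffected hand |
| Feet only | Dominant (tie) | Dominant | Both tests on an unaffected hand |

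The mismatch in rows 3 and 4 follows from the wording alone. Row 5 follows from entry naming no site. If the dominant hand is affected, the most affected hand is affected too, so at the level of the hand the cube can lose more participants than von Frey but never fewer.

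**Step 2. Illustrate the size.** The plan gives no alpha, power, effect size or SD for these measures, so there is no figure to reproduce. The only input from the documents is 48 per arm. Assumed: two-sided alpha 0.05; a true effect that would give 80% power if everyone could improve at the tested hand; no effect in participants with no deficit there; a constant SD.

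Standardised effect: d = (1.960 + 0.842) × √(2/48) = 0.572.

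Let f be the share with a deficit at the tested hand. The documents do not give f.

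- All randomised: effect f × d, 48 per arm, so power = Φ(f × 2.802 − 1.960).
- Only those with a deficit: effect d, 48 × f per arm, so power = Φ(√f × 2.802 − 1.960).

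| Share unaffected (1 − f) | Diluted effect | Power, all randomised | Power, restricted |
|---|---|---|---|
| 0% | 0.572 | 80% | 80% |
| 10% | 0.515 | 71% | 76% |
| 20% | 0.457 | 61% | 71% |
| 30% | 0.400 | 50% | 65% |
| 40% | 0.343 | 39% | 58% |
| 50% | 0.286 | 29% | 51% |

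For example, at f = 0.8: 0.8 × 2.802 − 1.960 = 0.281, giving 61%; √0.8 × 2.802 − 1.960 = 0.546, giving 71%.

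Because √f is at least f for any f up to 1, restriction does not lose power under these assumptions, despite the smaller sample.

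**Step 3. Check for bias.** The site rules are the same in both arms, and allocation is randomised. Testing a less suitable hand reduces the visible effect but does not favour either arm.

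**The case against.** The strongest reply is that the size is unknown and could be small. This stands. The documents give no distribution of neuropathy by site, and the mention of walking trouble describes questionnaire content, not who enrols. The von Frey wording also presumes that a hand is affected, although nothing requires it. The shrinkage in the table simply restates the assumed share, which is why the range starts at zero.

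A less affected hand is also not an unaffected one. In row 3 of the first table the dominant hand may still have room to improve, so treating it as contributing nothing would overstate the loss. This stands too.

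The cube is said to follow a previously described method, and a fixed finger keeps the site constant across visits. Whether the dominant hand is part of that method cannot be checked from the documents. Constancy is a real merit for a change score, but a hand chosen once at baseline keeps it.

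A reader might infer three stronger things:

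- **That unaffected skin is tested as a matter of course.** The documents show only that it can be, in some participants.
- **That the tested hand switches between visits and distorts the result.** Item 5 does not say when the hand is chosen, but a change-from-baseline response presupposes one site. The rule is also common to both arms, so re-choosing would mainly shift change within each arm. It is a reason to record the hand, not a separate defect.
- **That differing hands spoil a joint reading of the two tests.** No composite or joint analysis is planned.

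**Conclusion.** The concern holds as a loss of sensitivity in two secondary measures. It is certain from the text that both tests are hand-only, that their hand rules differ, and that entry does not require hand involvement. How many participants this touches is not known, so the power figures are illustrations resting on the assumed alpha, effect, constant SD and share.

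The comparison between arms is not biased. The primary outcomes (BPI-SF and FACT/GOG-Ntx) and the other Aim 2 measures, sleep and medication change, are unaffected. It would therefore go too far to conclude that Aim 2 as a whole, or the trial, is compromised. The change is still worth making because it is nearly free and the baseline information may not be reliably recoverable afterwards.

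**What to change.** 1. In items 5 and 6, under both Study Entry and Assessment Instruments, use one rule: choose the test hand once at baseline as the more affected hand (dominant if equal), record it, and use that hand for von Frey and for the cube at every visit. The cube stays on the index finger pad of that hand.
2. Record at baseline whether the hands are affected, by a stated definition such as reported numbness, tingling or pain in a hand.
3. In the Statistical Analysis section, prespecify an analysis of the two sensory tests in participants with baseline hand involvement, alongside the all-randomised analysis. Because the set is defined from baseline data, the comparison within it remains a randomised one.

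The cost is a wording change in two items (each stated twice), one baseline item and one added analysis, with no new visit or equipment. The downside is that the restricted analysis has fewer participants and says nothing about foot-only neuropathy, which would still have no sensory test at its own site. The report should say so.

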Participants will be asked to provide permission for us to contact their treating oncologist. The oncologist will be sent a letter, by fax, informing them of the study procedures and that their patient wishes to participate in this study. We will also request the patients' lab results (complete blood count and metabolic panel) so that subjects will not need to undergo another blood draw. If we are unable to obtain the labs from the oncologist, we will obtain a CBC and metabolic panel on subjects who agree to this. Potential volunteers with a history of cardiac disease, such as arrhythmia or a past myocardial infarction, will be excluded. Subjects with a history of orthostatic hypertension will also be excluded. Subjects with renal or hepatic insufficiency will not be included (liver function tests exceeding 2 x normal, BUN/CR > 22).

Subjects who are included will have been diagnosed with stage I, II or stage III breast cancer, and are no longer taking chemotherapy. The expected relative five-year survival for stage I and II is 93% and 72% for stage III.

The following medications, which are moderate or strong inhibitors, inducers, substrates of liver enzymes or drugs with high protein binding, will not be permitted: clarithromycin, itraconazole, erythromycin, fluconazole, clopidogrel, rifampin, sulfamethoxazole, warfarin, any opioids, warfarin, anti-epileptic medications (including carbamazepine, phenytoin, valproic acid, and gabapentin but excepting of clonazepam or diazepam).

The following medications will not be excluded, but will be flagged (as an alert for a potential interaction): fluvoxamine, fluoxetine, paroxetine, bupropion, duloxetine, melatonin, ramelteon, tasimelteon, theophylline, tizanidine, repaglinide, gemfibrozil, mirabegron, verapamil, indometacin, canagliflozin, flurbiprofen, ibuprofen, lumiracoxib, valdecoxib, nateglinide, troglitazone, ertugliflozin, oxazepam, lorazepam, diazepam, clonazepam.

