Participants who choose to attend all study visit will be given two weeks' worth of medication on each in-person lab visit. Participants who choose to opt out of the in-person visits of week 2 and 4 will receive 4 weeks of study medication. If participants who opt out of the weeks 2 and 6 in-person visits will still perform these visits virtually. While the TAC and mechanical sensitivity tasks will not be done, a study PI will still review their medications, concomitant medication use, and any adverse events.

All questionnaires will be obtained using Qualtrics.

Subjects will be asked to answer the following questionnaires daily:

1. Questions about taking their medication:
 - a) How many doses did you take today? (1, 2, or 3)
 - b) Have you made sure that no one else can access the dose? (yes or no)
2. The Brief Pain Inventory-Short Form (BPI-SF).
3. Promis Sleep Questionnaire.

On a weekly basis, subjects will be asked to complete the full FACT/GOG NTX (38 items).

In the lab visits, subjects will be asked to complete the following: Medication Questionnaire, the TAC, and mechanical sensitivity test. They will be seen by Drs. [name] or [name] to review their study medication. This will include a discussion of how well the medication was tolerated and whether there were any problem with the medication. We will also ask about concomitant medications subjects are taking. On the weeks that subjects are not seen in the lab they will be contacted by phone to ask about these same issues.

Cannabinoids:

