The cannabinoid capsules (two weeks' worth) will be provided during the visits. Subjects will begin with one capsule (100 mg CBD and 5 mg THC) in the evening. If the patient reports tolerating 1 capsule day for about 3 days, she will be instructed to take 2 capsules/day for several 3-5 days. If that is tolerated well, the dose will then be increased to three capsules per day. Participants will be encouraged to escalate doses on days they plan to be home in case they experience discomfort. The dose will then be increased to two and then three capsules per day, as long as these doses are tolerated well. The dose increase will occur over 7 to 10 days. Subjects who cannot tolerate more than one capsule per day can stay at that dose. Subjects who tolerate two a day will remain at that dose, and those who tolerate 3 capsules per day will be maintained at that dose. In our experience, there is a great degree in how non-cannabis smokers experience the intoxicating effects of THC, which is why subjects will self-titrate the effects. Thus, we expect that some subjects will take only one capsule daily, while others will take up to 3 a day. In a previous study by Tilray, performed in subjects undergoing chemotherapy and experiencing nausea and vomiting, subjects titrated up to 15 mg THC daily and 70% of subjects tolerate that dose.

Participants will be seen by a study investigator (Drs. [name] or [name]) at the laboratory visits. [name] is a board-certified psychiatrist. [name] is a psychologist with over 20 years of experience administering cannabis to research volunteers and managing neuropsychiatric side effects related to cannabinoids. The study assessments (TAC, mechanical sensitivity) may be done by other study personnel, but Drs. [name] or [name] will see the subjects at lab visits.

Blood samples will be drawn at weeks 4 and 8 to measure cannabidiol levels. Samples will be sent to [name] at The University of Utah who will perform the analysis, without identifying information.

Subjects will receive: 1) \$40 for the screening visit, 2) \$4 each day for completing the Qualtrics questionnaires; 3) \$30 for each of the baseline lab visit (virtual and in-person) and \$40 for each of the laboratory visits (weeks 2, 4 and 6, which last about 1 hour); 4) \$140 for the end of study laboratory visit (week 8, about 3 hours). Thus, the total is up to \$584.

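### Raised heart rate and hypotension are named as cannabis risks, but no blood pressure or heart rate is scheduled on treatment, and the orthostatic exclusion is worded in opposite directions

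*Combined protocol and SAP*

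**What the plan says.** **The risk.** Risks/Discomforts/Inconveniences, item 1, states: "Smoked cannabis can also cause increased heart rate and hypotension, and we will exclude volunteers with orthostatic hypotension". The same item says that the heart-attack risk with oral cannabinoids is unknown, and it lists dizziness, gait disturbance and sedation among the effects of THC.

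**The exclusion.** Exclusion 2 of the criteria table begins "Diagnosis of a major medical or neurological disorder, including hypertension or orthostatic hypotension, cardiovascular" and continues to other conditions. Its method of ascertainment is "Medical Assessment, laboratory studies, interview with a study physician". The Screening and Recruitment text says "Subjects with a history of orthostatic hypertension will also be excluded".

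**Measurement before treatment.** Of the in-person screening visit the protocol says: "This includes the ECG, physical exam, pregnancy test, and lab work".

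**Measurement on treatment.** The table introduced by "The schedule for the scales and tests at laboratory visits is as follows" has columns for the scales, in-person attendance, the tactile acuity cube, mechanical sensitivity and blood levels. The narrative says "In the lab visits, subjects will be asked to complete the following: Medication Questionnaire, the TAC, and mechanical sensitivity test", followed by an investigator's review of tolerability and concomitant medication. Under Cannabinoids: "Blood samples will be drawn at weeks 4 and 8 to measure cannabidiol levels".

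**Symptom follow-up.** There is a telephone call on the morning following the first dose, questions about side effects each week, and a route to contact the investigator between visits. Each dose increase depends on how the previous level was tolerated.

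**The concern.** The protocol takes the haemodynamic effect seriously enough to exclude volunteers because of it, yet it plans no measurement of it once dosing starts. The eligible group has grade 2 or 3 sensory neuropathy, and the listed THC effects include dizziness and gait disturbance. A participant's report of dizziness cannot by itself separate a postural fall in blood pressure from intoxication. A change without symptoms would not be reported at all.

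The trial is placebo-controlled, so it could compare blood pressure and heart rate between the oral combination and placebo. Without scheduled readings there is nothing to compare. The entry criterion tied to the same risk is also worded in two opposite ways, so two screeners reading different sections could apply it differently.

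**Working it through.** No formula in the plan bears on this point, and there is no stated figure to reproduce. The check sets the text side by side and counts.

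**Step 1: the exclusion wording.**

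| Place | Orthostatic condition excluded |
|---|---|
| Criteria table, exclusion 2 | hypotension (the row also lists hypertension) |
| Risks/Discomforts/Inconveniences, item 1 | hypotension |
| Screening and Recruitment | hypertension, by history |

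Two places agree and one differs. None of the three names a postural or resting blood pressure measurement as the means of deciding.

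**Step 2: what is named at each visit.**

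| Visit | In person | Content named | Blood pressure or heart rate named |
|---|---|---|---|
| In-person screening | yes | ECG, physical exam, pregnancy test, labs | no (exam and ECG may yield them) |
| Baseline | yes | scales, cube, filaments | no |
| Weeks 1, 3, 5, 7 | no | scales, telephone review | no |
| Weeks 2, 6 | optional | scales, clinical review; cube and filaments if attended | no |
| Weeks 4, 8 | yes | scales, cube, filaments, clinical review, blood draw for drug levels | no |

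Exclusion 4 adds a urine pregnancy test at lab visits for women of childbearing potential. In the text available, heart rate appears once, as a risk. Blood pressure and vital signs do not appear.

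**Step 3: count.** On-treatment weekly visits: 8. Visits with a named blood pressure or heart rate reading: 0. In-person on-treatment visits per participant: 2 (weeks 4 and 8) up to 4 (weeks 2, 4, 6 and 8).

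**Step 4: timing.** Dose escalation is planned over 7 to 10 days. Taking week 2 as day 14 and week 4 as day 28, with dosing started at baseline, the first in-person visit falls 14 − 10 = 4 days after the latest planned end of escalation. For a participant who opts out of week 2 it falls 28 − 10 = 18 days after. In-person readings would therefore describe the maintenance dose, not titration.

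**Step 5: analysis.** The Statistical Analysis section covers efficacy outcomes only and has no safety summary into which such readings would go.

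**The case against.** The strongest reply is that the risk is not left unattended. The plan has the call after the first dose, discussion of a lower dose when side effects go beyond tiredness and sleepiness, tolerability-based escalation, weekly enquiry, investigator review at lab visits, and discontinuation on clinical worsening. A reader might infer that exclusion at entry is the only safeguard, but these provisions rule that out. A reader might also suppose that a participant reporting dizziness would go home unmeasured. Nothing says so, and an investigator could take an unscheduled reading.

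Second, the protocol attributes the effect to smoked cannabis, and the study product is an oral capsule. That stands as a limit on how strongly the risk applies. It does not remove the point, because the protocol itself excludes on that ground.

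Third, the differing word may be a slip in one place. A reader might infer that people with orthostatic hypotension would be admitted. The documents do not support that: the criteria table still excludes them, and the Screening text adds an exclusion without withdrawing one. What remains is a contradiction to reconcile.

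Fourth, the schedule is not exhaustive. Its table omits the pregnancy test and the clinical review, so absence from it is weak evidence alone. But the narrative, which supplies those missing items, names no blood pressure or heart rate either.

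Finally, cuff readings at existing visits would miss the first dose and titration. That is correct and limits what the fix can deliver.

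**Conclusion.** The point holds in a limited form. The orthostatic exclusion is contradictory across three places. On treatment, the named risk is monitored by symptoms and not by scheduled measurement: 0 of 8 weekly visits carry a named blood pressure or heart rate reading. Asymptomatic changes would go undetected, and the arms could not be compared on measured values.

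It would go too far to say that the trial cannot detect any such effect, since symptomatic events can be picked up by enquiry. The documents give no event rate for the oral product, so the number of missed changes cannot be sized. The effect on eligibility is probably small. The primary outcomes and their analysis are untouched. The conclusion assumes that the visit table and narrative together state what is scheduled; readings taken by local habit, or within the screening physical exam, would soften it.

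This is a safety-reporting gap worth closing because the remedy is cheap. It is not a threat to the trial's validity.

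**What to change.** 1. Reconcile criteria table exclusion 2, the Screening and Recruitment text and Risks item 1, so that all three name the same orthostatic condition or conditions. The sponsor decides the rule.
2. Add a blood pressure and heart rate column to the visit schedule at baseline, weeks 4 and 8, and weeks 2 and 6 when attended in person. Record the time since the last dose with each reading. This gives 1 + 2 = 3 to 1 + 4 = 5 readings per participant who completes.
3. Add a short safety paragraph to Statistical Analysis stating that these readings, and their change from baseline, will be summarised by arm.
4. If the sponsor prefers not to measure, say so and give the reason.

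The cost is a few minutes per existing visit, one table column and a corrected exclusion. It also needs some closer contact than the COVID distancing default, which the blood draws at weeks 4 and 8 already require. The remaining limitation should be stated: daytime readings may miss the first dose, titration and the peak after evening dosing. Recording time since dose at least makes that visible.
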